## Recruitment and study workflow:

Acute care residents will be recruited and consented for a randomized control trial via email invitation and REDCap software. Participants will be asked to complete baseline measurements of simulation, anaphylaxis management, and immersive device (virtual reality or mixed reality) experience.

## Randomization and Study Groups

Randomization will be accomplished at the time of consent, to one of the two groups: A) HoloSIM based simulation (Intervention) or B) mannequin-based simulation (Control). Both groups will require students to learn and practice decision-making concepts for the management of anaphylaxis using their assigned modality (HoloSIM or traditional mannequin). Randomization will be stratified by specialty, as there is a potential for training background as a bias. We have chosen not to stratify by training level, due to data that both staff physicians and residents of all levels frequently have delayed or missed management steps when undergoing anaphylaxis simulations.

## Sample Size Calculation and Feasibility:

Power analysis was conducted in SealedEnvelope running an analysis for continuous outcome non-inferiority trial using a power of 0.9, alpha level of 0.05, and standard deviation calculated using RevMan software from a previous study utilizing the same anaphylaxis checklist evaluation tool. A non-inferiority limit of 3 out of a possible 45 total checklist points, equal to one major checklist criterion, was determined by investigator consensus to be significant. The items on the checklist are similar to those previously validated in earlier anaphylaxis simulation studies,. The required sample size was calculated as 28. We consider this feasible as an estimated 20 new residents rotate through the included services each month. To compensate for a 10-20% loss to follow-up and increased robustness for secondary outcomes, we will recruit a total of 40 participants (20 in each group) over a period of 12 months.

We have chosen a noninferiority comparison as we believe a finding of comparable efficacy for the HoloSIM platform in light of its potential advantages in telesimulation capabilities, scenario flexibility of mixed reality, and potential for cost effectiveness would be significant.

### Study Conduct and Data Collection:

Group A (Intervention). Participants randomized to Group A will arrive on day 0 to be given an orientation to the immersive HoloSIM platform. When they feel accustomed to its technical aspects an anaphylaxis management scenario will be initiated.

Group B (Control). Participants randomized to Group B will be assigned to mannequin-based scenario practice, which is the current gold standard in medical education and

assessment. Similar to the HoloSIM group, participants will arrive on day 0 to be given an orientation to the mannequin-based simulation environment so that they feel accustomed to its technical aspects. The anaphylaxis management scenario will match the HoloSIM environment and sequence of events.

All participants will receive learning objectives and a handout with educational content previously developed by a panel of allergists and be asked to review it approximately 48 hours prior to the intervention simulation session.

Participants will have access to the same handouts provided at the time on enrollment for debriefing after each practice session, as well as an instructor led debrief. All participants will then complete a validated assessment of learning satisfaction tool, the Modified Simulation Effectiveness Tool (SET-M, see Supplementary Figure 5) ; if HoloSIM is utilized, participants will complete usability questionnaires as in the first study phase.

## Study follow-up:

We will invite participants to return one month later to assess the impact of the intervention with a validated anaphylaxis knowledge test developed by allergists for use with the same curriculum included in our study and a mannequin-based anaphylaxis assessment scenario, the parameters of which were piloted in the first study stage utilizing HoloSIM. Participants from the intervention group (Group A) will be oriented to the mannequin simulation environment prior to managing the scenario as they will not have had previous exposure to this modality. All participant sessions will be video recorded and evaluated by two trained assessors. Scoring of the assessment scenario will involve a weighted checklist (See Supplementary Figure 6) of critical events similar to other validated anaphylaxis scoring tools and used in a previous similar trial. Scores in percentage points will be averaged between assessors, with a significant deviation being referred to a third assessor.

[figure not shown]

Figure 3: Study Design

Study limitations:

We understand that participants in Group B (Control) will be learning on and then assessed using the same modality (mannequin-based simulation), which creates an advantage for these participants. However, practice and assessments cannot be done on live patients, and the current gold standard is mannequin-based simulation training. Thus, there are no alternatives but to compare HoloSIM to mannequin-based simulation.

We acknowledge that no pretesting will be performed prior to the intervention, this is to avoid repeated exposure to anaphylaxis related content immediately prior to the intervention. However, we have randomized carefully to avoid bias.

## Statistical analysis:

Demographic characteristics of participants will be summarized with appropriate measures of central tendency and dispersion (count/percent for categorical data). The mean checklist scores in each group will be presented as mean/standard deviation and inferential testing will be done with the t-test. The inter-assessor agreement will be measured using the interclass correlation coefficient (ICC).

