### **Hypothesis/Research Questions:**

In this study we propose to refine and evaluate an innovative holographic medical crisis simulation technique which can be used both as an assessment tool and for teaching technical and nontechnical skills in a novel simulation curriculum.

Two main research questions will be addressed:

- 1. Does the novel simulation platform have sufficient usability for regular teaching and assessment use?
- 2. Is a mixed reality simulation platform curriculum non-inferior to the current teaching and assessment standard of high-fidelity mannequin-based crisis simulation in terms of student acquisition of technical and non-technical skills?

This study is the first known research initiative aiming to demonstrate that a mixed reality simulation training and assessment solution is usable and can improve decision making skills and management in a complex crisis scenario. We hypothesize the HoloSIM platform is non-inferior to traditional mannequin-based simulation in acquiring and assessing technical and non-technical skills in a model life threatening health condition (e.g. anaphylaxis).

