## Statistical Analysis:

SUS and mixed reality specific questionnaire results will be compiled in aggregate and descriptive statistics will be presented as frequencies. For the items of the SUS, the score will be calculated using Brooke's standard scoring method.

Second Research Question (Study Phase II): Evaluation of the novel mixed reality based anaphylaxis curriculum as a teaching and assessment tool

In the second study phase the HoloSIM platform will be incorporated into a novel anaphylaxis education and assessment curriculum and evaluated by randomized control trial. The primary outcome will be the impact on technical and nontechnical skill

acquisition as assessed by performance checklist; secondary outcomes include the scenario related declarative knowledge assessed by multiple choice quiz, as well as learner perceptions of the mixed reality assessment tool as measured by questionnaire. The nature, timing, and validity of these measurement tools is outlined below.

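### The trial is framed and sized as non-inferiority with a 3-point limit, but the only test named for the primary outcome is a t-test that is not tied to that limit

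*Protocol*

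**What the plan says.** Four places in the protocol bear on the primary comparison.

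- **Hypothesis/Research Questions.** The second research question is "Is a mixed reality simulation platform curriculum non-inferior to the current teaching and assessment standard", and the hypothesis is that HoloSIM is "non-inferior to traditional mannequin-based simulation in acquiring and assessing technical and non-technical skills".
- **Second Research Question (Study Phase II), outcomes.** The primary outcome is skill "acquisition as assessed by performance checklist; secondary outcomes include" knowledge and learner perceptions.
- **Sample Size Calculation and Feasibility.** The calculation is for a "continuous outcome non-inferiority trial using a power of 0.9, alpha level of 0.05". The limit is "A non-inferiority limit of 3 out of a possible 45 total checklist points". The required number is 28. On recruitment: "To compensate for a 10-20% loss to follow-up and increased robustness for secondary outcomes, we will recruit a total of 40 participants", 20 per group. The section then justifies the framing: "We have chosen a noninferiority comparison as we believe a finding of comparable efficacy for the HoloSIM platform".
- **Statistical analysis (Study Phase II).** The inference on the primary outcome is covered by one sentence: "The mean checklist scores in each group will be presented as mean/standard deviation and inferential testing will be done with the t-test".

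The last section gives no limit, null hypothesis, confidence interval, sidedness or rule for declaring non-inferiority. No other section links the t-test to the limit, and the protocol does not refer the reader to a separate analysis plan.

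**The concern.** A t-test of two group means, named without qualification, is normally a test of no difference. Its two possible results do not answer the question this trial asks:

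- **Not significant.** This is not evidence that HoloSIM is less than 3 points worse. It can arise simply because the comparison is imprecise.
- **Significantly lower with HoloSIM.** This does not show that the deficit exceeds 3 points. A small, precisely estimated deficit could be significant and still lie inside the limit.

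Only a result significantly in favour of HoloSIM would support non-inferiority by itself, and the trial is neither designed nor powered for that. An analyst who follows the section literally would run a primary test that does not address the primary hypothesis. Whether non-inferiority was shown would then be argued after the data are seen.

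**Working it through.** **Inputs from the protocol.** Limit 3 of 45 points; alpha 0.05 (sidedness not stated); power 0.9; required N 28, so 14 per group; recruitment 40, so 20 per group; loss 10-20%. Analysed totals are therefore 40 × 0.80 = 32, 40 × 0.90 = 36, or 40 (16, 18 or 20 per group). No standard deviation (SD) is given.

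**Step 1. The planned N.** Because the SD is not printed, N = 28 can only be inverted. With a true difference of 0,

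n per group = 2 × SD² × (z_alpha + z_power)² / 3², so SD = 3 × √(14/2) / (z_alpha + 1.282).

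- One-sided 0.05: 3 × 2.646 / (1.645 + 1.282) = 2.71 points.
- One-sided 0.025: 3 × 2.646 / (1.960 + 1.282) = 2.45 points.

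These are the upper ends. Allowing for rounding up to 14 per group, SDs of about 2.62-2.71 or 2.36-2.44 give 28. The figure is attainable but cannot be verified, and no error in it is alleged.

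**Step 2. The main result, which needs no SD.** At a true difference of 0, a two-sided 5% t-test of zero difference is significant in 5% of trials, half in each direction. It therefore significantly favours HoloSIM in 0.05 / 2 = 2.5% of trials at any N and any SD. The planned probability of concluding non-inferiority in that situation is 0.9.

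**Step 3. What a test tied to the limit would deliver.** Power at true equality, from the noncentral t with 2n - 2 degrees of freedom and noncentrality 3 / (SD × √(2/n)):

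| Analysed | SD 2.71, one-sided 0.05 | SD 2.45, one-sided 0.025 |
|---|---|---|
| 32 | 0.921 | 0.918 |
| 36 | 0.946 | 0.946 |
| 40 | 0.963 | 0.965 |

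So, under the SD implied by N = 28, the planned recruitment supports the analysis that the hypothesis calls for.

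**Step 4. Illustration: reading a non-significant result as non-inferior.** The protocol does not state this rule. It is the likely misuse of a zero-difference test. Take a true deficit of exactly 3 points, with noncentrality -3 / (SD × √(2/n)). The probability of a non-significant two-sided 5% test is:

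| Analysed | SD 2.71 | SD 2.62 | SD 2.45 | SD 2.36 |
|---|---|---|---|---|
| 32 | 14.3% | 12.0% | 8.2% | 6.5% |
| 36 | 10.3% | 8.4% | 5.4% | 4.1% |
| 40 | 7.4% | 5.8% | 3.5% | 2.5% |
| Test tied to the limit | 5% | 5% | 2.5% | 2.5% |

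With a one-sided 5% zero-difference test at SD 2.71 the rates are 7.9%, 5.4% and 3.7% against 5%, so the excess nearly vanishes at 36 and reverses at 40. If the SD were 4-5 points (an assumption outside what N = 28 implies), the two-sided rate at 40 analysed would be 36-54%.

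**Step 5. Results on which the two readings disagree.** At an observed SD of 2.71, with SE = 2.71 × √(2/n), the two-sided test is non-significant if the observed deficit is below t(0.975) × SE. Non-inferiority at one-sided 0.05 requires a deficit below 3 - t(0.95) × SE.

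| Analysed | Non-significant if deficit below | Non-inferior if deficit below | Band of disagreement |
|---|---|---|---|
| 32 | 1.96 | 1.37 | 1.37 to 1.96 |
| 36 | 1.84 | 1.47 | 1.47 to 1.84 |
| 40 | 1.74 | 1.55 | 1.55 to 1.74 |

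**Step 6. Scale.** The Study follow-up section has scores in percentage points, while the limit is in points of 45. On the percentage scale the limit is 3 / 45 = 6.67 percentage points.

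**The case against.** The strongest reply is that this is brevity, not error. The analysis section never mentions a zero difference or superiority. A t-test is a standard tool for a non-inferiority comparison once the null is shifted by the limit. Read together with the hypothesis and the sample size section, the sentence can be taken in that sense, and the exact null, interval and conclusion rule are often left to an analysis plan that is not at hand here. The limit is prespecified, and means and SDs will be reported, so a reader who knows the group sizes could compute the interval.

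The numerical harm can also be called modest. Step 4 needs an SD and a decision rule that the protocol does not state. At the lower SDs compatible with N = 28, the excess at 40 analysed is under one percentage point or nil. The band in Step 5 is about 0.2 points wide at full recruitment.

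Much of this stands. The wording does not exclude a correct analysis, and Steps 4 and 5 are illustrations only. What does not stand is the claim that nothing is wrong. The protocol has its own analysis section, names the test there, and does not defer to another document. The named test, on its ordinary reading, does not match the hypothesis and sample size of the same protocol. That a reader can apply the limit afterwards does not replace a prespecified rule, particularly with sidedness unstated and the limit on a different scale from the scores.

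**Conclusion.** The concern holds. The protocol names a primary test that, as ordinarily understood, cannot answer its own primary question when the two groups perform alike. The size that rests on no assumption about variability is 2.5% against 0.9: the chance at true equality that a two-sided zero-difference test significantly favours HoloSIM, against the planned chance of concluding non-inferiority. Inflated false claims (up to 14.3% against 5% at 32 analysed) depend on the back-solved SD and on misreading non-significance, and they shrink or vanish at full recruitment. Because the defect sits in the primary inference and one sentence does not settle which test is meant, it should be corrected before any data are analysed. Nothing here shows that N = 28 or the recruitment of 40 is wrong.

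**What to change.** Replace the t-test sentence in Statistical analysis (Study Phase II) with wording such as:

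> The primary analysis estimates the HoloSIM minus mannequin difference in mean checklist score with a t-based confidence interval (equivalently, a t-test of the null hypothesis that the difference is -3 points or lower). Non-inferiority is concluded only if the lower confidence limit lies above -3 of 45 points (-6.67 percentage points if scores are analysed as percentages). A non-significant test of zero difference is not evidence of non-inferiority.

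The sponsor must also confirm the sidedness of the alpha used in the sample size calculation and use the matching interval: two-sided 90% if alpha was one-sided 0.05, two-sided 95% if it was one-sided 0.025. Stating the SD used would let N = 28 be checked.

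The cost is wording only. Sample size, data collection and design stay as they are.

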## Recruitment and Study Groups:

Participants from acute care postgraduate training programs at Sunnybrook Health Sciences Centre, a tertiary academic institution, will be recruited for 1-hour sessions via email invitation. Consent will be obtained via REDCap at the time of recruitment, as well as a questionnaire to survey demographic information and previous experience with simulation and immersive reality technologies. This will include resident learners of all levels, recruited to use the software in the student role while paired with staff physicians (i.e. instructors/assessors) from the same specialty using the software in the instructor role, drawn together from the same fields of Anesthesiology (Group 1), Internal Medicine (Group 2), Critical Care Medicine (Group 3), or Emergency Medicine (Group 4).

Instructors will be informed two weeks in advance that the session content will include time for orientation to mixed reality, free experimentation, an anaphylaxis scenario, as well as a scenario of their choosing drawn from a study generated database of publicly available peer reviewed content within their specialty, , .

Usability evaluation:

The pairings will use HoloSIM to conduct medical crisis simulations in both a structured and unstructured manner. Usability will be assessed in an ethnographic manner using audio recorded semi-structured interviews with thematic analysis. Usability will also be assessed via the System Usability Scale(SUS), a widely cited, validated, and industry standard Likert scale questionnaire (see Supplementary Figure 4) utilized across a variety of software platforms. No validated tools exist to specifically assess mixed reality software, however a comprehensive multidomain Likert questionnaire, will be administered (previously developed to assess a mixed reality medical simulation learning tool) to students to delineate factors that enhance or limit learning via the Hololens 2 headset and HoloSIM. Additional Likert items will assess the participants age, previous experience with simulation-based teaching, and their desired frequency of future use of the platform.

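### Randomisation is stratified by specialty but the primary comparison is a plain t-test, which gives up precision if specialty affects the checklist score

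*Protocol*

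**What the plan says.** In Randomization and Study Groups (Phase II), the protocol states: "Randomization will be stratified by specialty, as there is a potential for training background as a bias". The primary outcome is technical and nontechnical skill "acquisition as assessed by performance checklist".

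The Phase II Statistical analysis section reports the checklist scores by group as mean and standard deviation and adds that "inferential testing will be done with the t-test". It mentions no stratum term, stratified test or covariate, and neither does any other part of the protocol.

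The Sample Size section sets a margin of 3 of 45 points, "using a power of 0.9, alpha level of 0.05", and concludes: "The required sample size was calculated as 28". Forty are to be recruited, 20 per group, to allow for 10-20% loss. The SD used is not printed, and alpha is not said to be one- or two-sided.

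**The concern.** The design treats specialty as a possible source of score differences and controls it at randomisation. The stated analysis then ignores it.

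When arms are balanced within specialty, differences between specialties cancel out of the arm comparison, so the true sampling error of the mean difference is smaller. A pooled two-sample t-test still counts those differences as noise within each arm. If specialty affects the score, the test's standard error is too large: the interval is wider than it needs to be, and the actual type I error falls below nominal. False claims of non-inferiority do not become more frequent. What is lost is the chance of showing non-inferiority when it is true.

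This matters most when HoloSIM is truly a little worse or the SD is larger than planned. The protocol makes the first plausible. In its study limitations it concedes that controls learn and are assessed on the same modality, "which creates an advantage for these participants". There is also no pretest, so no baseline score is available to sharpen the comparison. The argument applies to specialty only. For experience items not used in stratification, the unadjusted standard error is valid.

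**Working it through.** **Inputs from the protocol.** Margin 3 points; power 0.9; alpha 0.05; required number 28, read as the total (14 per arm); 40 recruited 1:1; loss 10-20%. With 20% loss, 40 × 0.8 = 32 evaluable.

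**Inputs assumed.** SD as below. Four equal strata, borrowed from the four specialties listed for Phase I, because Phase II says only acute care residents. Specialty explains a share R² of 0-30% of the score variance. Arms are balanced 1:1 within specialty.

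**The plan's own figure.** The 28 cannot be checked directly because the SD is not given. Solving n per arm = 2·SD²·(z_α + z_β)²/margin² backwards at a true difference of zero:

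- one-sided 0.05: SD = √[14 × 9 / (2 × (1.645 + 1.282)²)] = 2.71
- one-sided 0.025: SD = √[14 × 9 / (2 × (1.960 + 1.282)²)] = 2.45

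The point does not depend on whether 28 is right.

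**By formula, 32 evaluable, SD 2.71, R² = 0.2.**

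- t-test 90% half-width ≈ t(30) × SD × √(2/16) = 1.697 × 2.71 × 0.3536 = 1.63
- adjusted ≈ t(27) × SD × √(1 − R²) × √(2/16) = 1.703 × 2.71 × 0.894 × 0.3536 = 1.46
- actual level of the t-test: its cut-off of 1.697 nominal standard errors is 1.697/0.894 = 1.90 true standard errors, an upper-tail probability of about 3.4% instead of 5%

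**By simulation.** 60,000 trials per setting; equally spaced specialty means scaled to the stated share; pooled t-test against a linear model on arm and specialty. Type I error is taken at a true difference of −3. Each cell is t-test / adjusted.

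| Specialty share | 90% CI half-width | Type I error | Power at 0 | Power at −1 |
|---|---|---|---|---|
| 10% | 1.62 / 1.54 | 4.1% / 4.9% | 93% / 94% | 66% / 69% |
| 20% | 1.63 / 1.45 | 3.2% / 5.0% | 94% / 96% | 66% / 73% |
| 30% | 1.63 / 1.35 | 2.5% / 5.0% | 95% / 98% | 67% / 78% |

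The interval narrows by about 5% (1.54/1.62), 11% (1.45/1.63) and 17% (1.35/1.63). At a share of 0% the adjusted interval is about 0.3% wider and power at 0 is 92% either way.

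**Sensitivity at a 20% share, power at 0 (t-test / adjusted).**

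- SD 2.0: 99.7% / 99.8%. SD 3.5: 79% / 84%. SD 4.5: 58% / 66%.
- SD 2.71 with 28 evaluable: 91% / 94%. With 36: 96% / 98%. With 40: 98% / 99%.
- Alpha read as two-sided (SD 2.45): 95% half-width 1.77 / 1.57; power 94% / 96%.

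The relative narrowing hardly changes with two, three or four strata, or with unequal strata of 16/8/4/4.

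**Relaxing exact balance.** A further simulation (12,000 trials per setting) randomised 40 and lost 8 at random.

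- Blocked within specialty: at shares of 10%, 20% and 30% the t-test's type I error is 4.4%, 3.5% and 3.2%, and adjustment narrows the interval by about 4%, 10% and 16%. At a share of 0% the adjusted interval is about 1.3% wider.
- Not blocked: type I error is 4.8-5.4%, so the test is no longer conservative. Narrowing is about 0%, 6% and 12%. At a share of 0% the adjusted interval is about 6% wider, and power at 0 falls from 92% to 89%.

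**The case against.** Stratum terms are often settled in the SAP, which is not to hand, and the protocol's analysis section is only an outline. That would answer a silent protocol, but this one names the test. An SAP that adjusted for specialty would have to depart from it.

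The t-test is valid, and at the planning case it meets both the stated alpha and the stated power. The protocol gives bias, not precision, as its reason to stratify, and balance alone serves that purpose. All this is true and limits the weight of the point. It does not make the unadjusted analysis the better choice.

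The strongest objection is that conservatism requires balance within specialty, and the protocol describes no blocking. With unrestricted allocation inside strata the t-test is at its nominal level, and adjustment costs something if specialty is irrelevant. That condition has to be stated. Even so, stratified allocation without any restriction would achieve nothing, so balance is the natural reading, and random loss after blocked allocation reduces the gain only slightly.

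Finally, nothing in the protocol shows that specialty affects this score; it speaks only of a potential. The largest gains need both a 30% share and an assumed 1-point deficit.

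**Conclusion.** The point holds as a modest loss of precision, with no loss of validity. It depends on specialty affecting the score, and the conservatism also depends on arms being balanced within specialty.

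Under the assumed SD of 2.71, four strata and 32 evaluable participants, the t-test costs 1 to 3 points of power at a true difference of zero and 3 to 11 points at a true 1-point deficit, for specialty shares of 10-30%. If the SD is 3.5 or 4.5 rather than the implied value, power at zero is below 0.9 under either analysis, and adjustment recovers 5 or 8 points at a 20% share. The SD, the number of Phase II strata and the variance share are all assumptions, so these figures are a range and not an estimate.

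**What to change.** Reword the Phase II Statistical analysis section so that the primary analysis is a linear model of the one-month checklist score on arm and specialty, using the strata as randomised. Compare the confidence limit of the adjusted mean difference (HoloSIM minus mannequin) with the non-inferiority margin, both on the same scale. Keep the t-test as a sensitivity analysis. State how allocation is balanced within specialty.

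Anaphylaxis-management experience, already collected at baseline under Recruitment and study workflow, could be added as a prespecified covariate for precision and chance imbalance. Its gain was not quantified because the protocol does not say how it is scaled.

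The cost is analysis wording only, since specialty is known at randomisation. With four strata the model uses about 3 more degrees of freedom. If specialty turns out not to matter, the interval is 0.3-1.3% wider under blocked allocation. A specialty with evaluable participants in only one arm contributes nothing to the adjusted difference.
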